7.2.4.5.3. Central Nervous System

Central nervous system toxicity appears to be dose dependent, and is variable in onset, but usually resolves when ifosfamide is discontinued. Incidence is higher with higher doses, concomitant use of aprepitant, electrolyte imbalances, renal/ hepatic impairment or preexisting CNS disorders. It may manifest as transient mental status changes (somnolence, confusion, hallucination, disorientation, and lethargy), cerebellar dysfunction, extrapyramidal symptoms, transient weakness, cranial nerve dysfunction or seizure activity. Methylene blue, which may act as an electron acceptor or decrease chloracetaldehyde formation, has been suggested as treatment or prophylaxis of ifosfamide induced encephalopathy.

7.2.4.5.4. Other Toxicities

General guidelines for ifosfamide dose modification are shown in [Table JGDN.7.13](#). Dose modifications of ifosfamide due to hepatic impairment are shown in [Table JGDN.7.14](#).

Table JGDN.7.13. General Guidelines for Dose Modification of Ifosfamide due to Toxicity

Worst Toxicity /Counts in Previous Cycle	Ifosfamide Dose Reduction ^a
Febrile neutropenia	First episode: maintain full dose and include GCSF at subsequent cycles. Subsequent episodes: Decrease 20%
Platelets <75,000/mm ³	If less than 1 week duration: maintain full dose If greater than 1 week duration: Decrease 20%
Thrombocytopenic bleeding	Decrease 20%
Somnolence or other signs of encephalopathy	Hold; methylene blue 50 mg intravenous every 4 hours until resolution. Consider prophylactic methylene blue for subsequent cycles. Consider discontinuing or dose reduction for next cycle.
Grade 3 related organ / nonhematologic	Decrease 20%
Grade 3 or 4 neurotoxicity	Discontinue
Grade 4 related organ / nonhematologic	Discontinue

a Do not retreat until absolute neutrophil count $\geq 750/\text{mm}^3$, platelets $\geq 75,000/\text{mm}^3$ and toxicity recovered to \leq Grade 2.

Table JGDN.7.14. Dose Modification of Ifosfamide due to Hepatic Impairment

Bilirubin		AST/ALT	Ifosfamide Dose Reduction*
1-2 X ULN		<2 X ULN	Full dose
2-4 X ULN	And/or	2-5 X ULN	75% of initial dose
>4 X ULN		>5 ULN	Discontinue

Abbreviations: ALT = alanine aminotransferase; AST = aspartate aminotransferase; ULN = upper limit of normal.

a Based on clinical judgment – less conservative adjustments can be considered if hepatic changes are secondary to metastases rather than hepatic cirrhosis or hepatitis.

7.3. Method of Assignment to Treatment

Patients who meet all criteria for enrollment will be assigned to receive olaratumab in this study. Before each patient's enrollment into the study, an eligibility check must be conducted between the investigational site and the Lilly clinical research personnel to confirm that each patient meets all enrollment criteria. Upon confirmation of eligibility, the site will register the patient by assigning the patient a unique study identification number via the Interactive Web Response System (IWRS), which is accessible 24 hours a day. Study drug will be allocated to patients using the IWRS. No dose escalations (that is, initiating Parts B and C for a chemotherapy combination) can occur without prior discussion and agreement with the responsible Lilly CRP or CRS.

In Part A, if investigators have eligible patients who have consented concurrently, more than 3 patients may be entered for a particular chemotherapy combination provided that accrual has not ceased due to excessive toxicity. This enrollment procedure is allowed because of the advanced disease state of this patient population and the screening involved in defining eligibility. This event should be approved by the sponsor following discussions with the investigators.

7.4. Blinding

This is an open-label study.

7.5. Concomitant Therapy

All concomitant medications should be recorded throughout the patient's participation in the study.

Concomitant medications and supportive care therapies must also be documented at the time of discontinuation and at the 30-day short-term follow-up visit.

With the exceptions listed in the sections below, no other chemotherapy, investigational medications, other anticancer therapy, immunotherapy, hormonal cancer therapy, radiation, or surgery for cancer will be permitted while patients are on study treatment. Palliative radiotherapy (of ≤ 14 calendar days, e.g., for a solitary skeletal metastasis) after Cycle 7 may be allowed as long as the patient has not developed another reason for study discontinuation and other sites of disease are available for response assessment. Palliative radiation may not occur prior to discussion with the study medical monitor and written approval.

Appropriate documentation for all forms of premedications, supportive care, and concomitant medications (for example, medications such as sedatives, antibiotics, analgesics, antihistamines, corticosteroids, erythropoietin; procedures such as paracentesis, thoracentesis; or blood products such as blood cells, platelets, fresh frozen plasma transfusions) must be captured on the eCRF.

If premedication is required prior to the chemotherapy infusion, this must be done after the completion of olaratumab infusion, not before the olaratumab infusion.

7.5.1. Supportive Care

Patients should receive full supportive care, if necessary. Patients will receive supportive care as judged by their treating physician. If it is unclear whether a therapy should be regarded as supportive care, the investigator should consult the Lilly CRP. Use of any supportive care therapy must be captured on the eCRFs.

7.5.1.1. Dexrazoxane

For patients in the doxorubicin combination arm, dexrazoxane may be administered starting with the first dose of doxorubicin at the investigator's discretion according to instructions provided in the Pharmacy Manual for this study, beginning within 30 minutes prior to each doxorubicin infusion for the prevention of cardiotoxicity. It is recommended that all patients receiving doxorubicin receive dexrazoxane. Investigators should consult the dexrazoxane information provided in the Pharmacy Manual for this study for administration information (including warnings, precautions, contraindications, adverse reactions, and dose modifications).

Note that as the dose of dexrazoxane administered is dependent on the dose of doxorubicin administered, any dose modifications to doxorubicin will require a corresponding dose modification to dexrazoxane in order to maintain a dosage ratio of 10:1 (dexrazoxane:doxorubicin).

7.5.1.2. Mesna

For patients in the ifosfamide arm, mesna should be administered at a minimum dose equal to 60% of the ifosfamide dose according to institutional guidelines, including divided dose or continuous infusion.

Note that as the dose of mesna administered is dependent on the dose of ifosfamide administered, any dose modifications to ifosfamide will require a corresponding dose modification to mesna in order to maintain the correct dosage (mesna = minimum 60% ifosfamide).

7.5.1.3. Hydration

Ifosfamide should be given with extensive hydration consisting of oral or intravenous fluid (2 L/m² IV) to prevent bladder toxicity or according to institutional guidelines. The criteria to start chemotherapy may also include a urine-specific gravity < 1.010 or according to institutional guidelines.

7.5.1.4. Granulocyte-Colony Stimulating Factors and Erythroid Growth Factors

Following the first dose of combination chemotherapy, the use of G-CSFs such as Neulasta[®] (pegfilgrastim) and erythroid stimulating factors (for example, erythropoietin) are permitted,

including prophylactic use, during investigational therapy at the discretion of the investigator or according to ASCO guidelines (Smith et al. 2006) and NCCN guidelines (NCCN 2015).

7.5.1.5. Transfusion of Blood Products

Transfusions of red blood cells, platelets, or other blood products are permitted at the investigator's discretion, but may not be used to meet hematologic criteria for inclusion in the study (refer to Section 6.1.1, Inclusion Criterion [6]).

7.5.1.6. Antiemetic Therapy

Both prophylactic and symptom-directed anti-emetic therapy are recommended and should be used in accordance with institutional guidelines (when existent) and/or at investigator's discretion.

7.5.2. Prohibited Therapies

Additional concurrent chemotherapy, radiation therapy, biologic response modifiers, or other investigational or approved anticancer agents may not be administered to patients on this study. Palliative radiotherapy (of ≤ 14 calendar days, e.g., for a solitary skeletal metastasis) after Cycle 7 may be allowed as long as the patient has not developed another reason for study discontinuation and other sites of disease are available for response assessment. Palliative radiation may not occur prior to discussion with the study medical monitor and written approval.

7.5.2.1. Effect of CYP3A4, CYP2D6, and P-gp Inhibitors and Inducers on Doxorubicin

Doxorubicin is a major substrate of cytochrome P450 (CYP)3A4 and CYP2D6, and P-glycoprotein (P-gp). Clinically significant interactions have been reported with inhibitors of CYP3A4, CYP2D6, and/or P-gp, resulting in increased concentration and clinical effect of doxorubicin. Inducers of CYP3A4 (for example, phenobarbital, phenytoin, and St. John's Wort) and P-gp inducers may decrease the concentration of doxorubicin. Avoid concurrent use of doxorubicin with inhibitors and inducers of CYP3A4, CYP2D6, or P-gp. Refer to [Attachment 9](#) for a list.

7.6. Treatment Compliance

Study drugs will be administered intravenously at the investigational site, under the direction of the investigator. As a result, a patient's compliance with study drug administration is ensured. Patients should attend scheduled clinic visits and must comply with study criteria under their control. Deviation(s) from the prescribed dosage regimen should be recorded on the eCRF.

7.6.1. Evaluable Patients

Patients who withdraw from the study before receiving study drug(s) will be replaced and will not be included in the safety or efficacy assessments. Safety analyses will be conducted on all patients who have been exposed to study drug, regardless of whether they are deemed evaluable for other assessments.

Any patient from Parts A or B who is discontinued from the study before completing 1 cycle of olaratumab treatment will be deemed non-evaluable for assessment of olaratumab monotherapy, unless the patient experiences a DLT prior to withdrawal. Any patient who is discontinued from the study before completing 1 cycle of combination chemotherapy treatment (Cycle 2 for Parts A or B or Cycle 1 for Part C) will be deemed non-evaluable for assessment of a combination chemotherapy, unless the patient experiences a DLT or DLE-equivalent prior to withdrawal.

If a patient from Parts A or B is noncompliant during Cycle 1 due to reasons other than drug-related toxicity, he or she will be considered non-evaluable for olaratumab monotherapy and may be replaced. If a patient from Parts A or B is noncompliant during Cycle 2 or a patient from Part C is noncompliant during Cycle 1 due to reasons other than drug-related toxicity, he or she will be considered non-evaluable for combination chemotherapy and may be replaced.

Nonevaluable patients may be replaced to ensure that enough patients complete 1 cycle of olaratumab monotherapy or combination chemotherapy, unless accrual to that cohort has stopped due to a DLT.

Patients who are not evaluable for pharmacokinetics, but who complete 1 cycle of olaratumab monotherapy or 1 cycle of combination chemotherapy, may be replaced to ensure adequate PK data, unless accrual to that cohort has stopped due to a DLT.

8. Safety, Pharmacokinetic, Pharmacodynamic, and Efficacy Data Collection

8.1. Safety Evaluations

The safety and tolerability of olaratumab have been assessed in nonclinical toxicology and clinical studies and the results from these studies are detailed in the IB. This Phase 1 study contains detailed safety monitoring that will permit initial characterization of the safety profile of olaratumab in pediatric patients. Study procedures and their timing, including collection of blood and urine samples, are described in the Study Schedule ([Attachment 1](#)).

Standard laboratory tests, including chemistry, hematology, coagulation and urinalysis panels, will be performed. A serum pregnancy test will be administered if applicable. Other clinical laboratory tests will also be collected. [Attachment 2](#) lists the specific tests that will be performed for this study.

8.1.1. Safety Data Collection and Review

Investigators are responsible for monitoring the safety of patients who have entered into this study and for alerting Lilly or its designee to any event that seems unusual, even if this event may be considered an unanticipated benefit to the patient.

The investigator is responsible for the appropriate medical care of the patient during the study.

The investigator remains responsible for following, through an appropriate health care option, AEs that are serious, considered related to study treatment or the study, or that caused the patient to discontinue before completing the study. The patient should be followed until the event is resolved, the event is no longer considered to be drug-related, the event becomes stable or returns to baseline, a new treatment is initiated for the patient, or the patient dies or is lost to follow-up. Frequency of AE and serious adverse event (SAE) follow-up evaluation is left to the discretion of the investigator.

The timing of all safety evaluations is shown in the Study Schedule ([Attachment 1](#)).

[Table JGDN.8.1](#) presents a summary of AE and SAE reporting guidelines. [Table JGDN.8.1](#) also shows which database or system is used to store AE and SAE data.

8.1.2. Adverse Events

Lilly has standards for reporting AEs that are to be followed regardless of applicable regulatory requirements that may be less stringent. A clinical study AE is any untoward medical occurrence in a patient or clinical investigation subject administered a pharmaceutical product and which does not necessarily have a causal relationship with this treatment. An AE can therefore be any unfavorable and unintended sign (including an abnormal laboratory finding), symptom, or disease temporally associated with the use of medicinal (investigational) product, whether or not it is related to the medicinal (investigational) product. Any clinically significant findings from labs, vital sign measurements, and so on, that occur should also be reported to Lilly or its

designee as an AE. Lack of drug effect is not an AE in clinical studies because the purpose of the clinical study is to establish drug effect.

The investigator, monitor, and sponsor will review the collected data regularly for evidence of AEs. All patients will be assessed routinely for AEs as outlined in the study schedule. All AEs observed will be graded using CTCAE v 4.0.

The NCI-CTCAE v 4.0 will serve as the reference document for choosing appropriate terminology for, and grading the severity of, all AEs and other symptoms. All AEs observed will be graded using CTCAE v 4.0. Any minor version of CTCAE v 4.0 (for example, version 4.0X) may be used for this study. Minor CTCAE v 4.0 updates from the NCI will not necessitate a protocol amendment. For AEs without matching terminology within the NCI-CTCAE v 4.0 criteria, the investigator will be responsible for selecting the appropriate system organ class and assessing severity grade based on the intensity of the event. Note that both CTCAE term (actual or coded) and severity grade must be selected by study site personnel and collected on the eCRF. This collection is in addition to verbatim text used to describe the AE.

In addition to collecting the AE verbatim, the CTCAE term, and the CTCAE severity grade, AE verbatim text will also be mapped by the sponsor or designee to corresponding terminology within the Medical Dictionary for Regulatory Activities (MedDRA™) dictionary.

Cases of pregnancy that occur during maternal or paternal exposures to study drug should be reported. Data on fetal outcome and breastfeeding should be collected, if feasible, for regulatory reporting and drug safety evaluation.

Upon documentation of pregnancy, the patient must be removed from the study and treatment with study drug(s) must be stopped immediately.

For all enrolled patients, study site personnel will record the occurrence and nature of each patient's preexisting condition(s), including clinically significant signs and symptoms of the disease under treatment in the study. While the patient is on study, site personnel will record any change in these preexisting condition(s) and the occurrence and nature of any AEs. In addition, all AEs related to protocol procedures are reported to Lilly or designee.

If a patient's dosage is reduced or treatment is discontinued as a result of an AE, study site personnel must clearly report to Lilly or its designee via eCRF the circumstances and data leading to any such dosage reduction or discontinuation of treatment.

Investigators will be instructed to report to Lilly or its designee their assessment of the potential relatedness of each AE to protocol procedure or study drug via eCRF.

The investigator decides whether he or she interprets the observed AEs as either related to disease, study medication, study procedure, or other concomitant treatment or pathologies. To assess the relationship of the AE to the study drug, the following terminologies are defined:

- **Related:** a direct cause and effect relationship between the study treatment and the AE is likely.

- **Possibly related:** a cause and effect relationship between the study treatment and the AE has not been demonstrated at this time and is not probable, but is also not impossible.
- **Unrelated:** without question, the AE is definitely not associated with the study treatment.

As per Lilly's standard operating procedures, all "related" and "possibly related" AEs and SAEs will be defined as related to study drug.

8.1.2.1. Serious Adverse Events

Serious adverse event collection begins after the patient has signed informed consent and has received study drug. If a patient experiences an SAE after signing informed consent, but prior to receiving study drug, the event will not be reported as serious unless the investigator feels the event may have been caused by a protocol procedure.

Planned surgeries should not be reported as SAEs unless the underlying medical condition has worsened during the course of the study.

Planned hospitalizations or elective procedures for underlying preexisting conditions that are already recorded in the patient's medical history at the time of study enrollment should not be considered SAEs. Hospitalization or prolongation of hospitalization without a precipitating clinical AE (for example, for the administration of study therapy or other protocol-required procedure) should not be considered SAEs.

An SAE is any adverse event during this study that results in one of the following outcomes:

- death
- initial or prolonged inpatient hospitalization (except for study drug administration)
- a life-threatening experience (that is, immediate risk of dying)
- persistent or significant disability/incapacity
- congenital anomaly/birth defect
- considered significant by the investigator for any other reason

Important medical events that may not result in death, be life-threatening, or require hospitalization may be considered SAEs when, based on appropriate medical judgment, they may jeopardize the patient and may require medical or surgical intervention to prevent one of the outcomes listed in this definition.

Serious adverse events due to disease progression, including death, should not be reported unless the investigator deems them to be possibly related to the study drug.

Study site personnel must alert Lilly or its designee of any SAE within 24 hours of investigator awareness of the event via a sponsor-approved method. If alerts are issued via telephone, they are to be immediately followed with official notification on study-specific SAE forms. This

24-hour notification requirement refers to the initial SAE information and all follow-up SAE information.

If an investigator becomes aware of SAEs occurring after the patient's participation in the trial has ended, and the investigator believes that the SAEs are related to a protocol procedure or study drug, the investigator should report the SAEs to the sponsor, and the SAEs will be entered in the Lilly Safety System.

Information on SAEs expected in the study population independent of drug exposure and that will be assessed by the sponsor in aggregate periodically during the course of the trial may be found in the IB.

For recommendations on reporting SAEs, see [Attachment 5](#).

8.1.2.2. Adverse Event and Serious Adverse Event Reporting

Data on SAEs that occur before the end of trial will be stored in the collection database and the Lilly Safety System.

8.1.2.2.1. Prior to Administration of Study Drug(s)

During screening, all AEs and SAEs (regardless of relatedness to protocol procedures) are collected after the patient has signed the ICF. For patients who do not enroll in the trial (that is, have not received at least 1 dose of olaratumab), only AEs and SAEs related to protocol procedures are required to be reported.

8.1.2.2.2. On Therapy

All AEs and SAEs, regardless of relatedness to study drug(s) or protocol procedures, occurring while the patient is receiving study drug must be reported to Lilly or its designee. A patient is considered to be receiving study drug from the time he/she receives the first dose of study drug to when he/she receives the last dose of study drug.

8.1.2.2.3. Follow-Up Visit

All AEs and SAEs, regardless of relatedness to study drug(s) or protocol procedures, occurring during the follow-up visit (Visit 801) must be reported to Lilly or its designee. The follow-up visit (Visit 801) starts one day after the decision is made to discontinue the patient from the study. At the end of the follow-up visit, the patient will be required to have specific safety assessments ([Attachment 1](#)). The timing of these safety assessments is 30 days \pm 7 days after the decision is made to discontinue the patient from the study.

Following the safety assessments, which mark the end of the follow-up visit (Visit 801), the patient will be discontinued from the study, unless there is an ongoing AE or SAE that is possibly related to study drug. In this instance, the patient should be followed in subsequent long-term follow-up visits until the event is resolved, the event is no longer considered to be drug-related, the event becomes stable or returns to baseline, a new treatment is initiated for the patient, or the patient dies or is lost to follow-up.

If it is deemed to be in the best interest of the patient to start a new anticancer treatment prior to the scheduled end of the follow-up visit, the follow-up visit duration may be shortened. In this case, the follow-up assessments should be completed prior to the initiation of the new therapy.

After the follow-up visit (Visit 801), AEs are not required to be reported unless the investigator feels the AEs were related to either study drug, drug delivery system, or a protocol procedure. If an investigator becomes aware of an SAE believed to be related to protocol procedures or study drug, the investigator should report the SAE to the sponsor, and the SAE will be entered in the Lilly Safety System.

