screen	The act of determining if an individual meets minimum requirements to become part of a pool of potential candidates for participation in a clinical trial. In this study, screening involves invasive or diagnostic procedures and/or tests (for example, diagnostic psychological tests, x-rays, blood draws). For this type of screening, informed consent for these screening procedures and/or tests shall be obtained; this consent may be separate from obtaining consent for the study.
screen failure	A patient who does not meet one or more criteria required for participation in a trial
SD	stable disease
sponsor	The party who takes responsibility for the initiation, management and/or financing of a clinical study.
STS	soft tissue sarcoma
study completion	This study will be considered complete after all patients have completed treatment and their safety summary visit.
SUSAR	suspected unexpected serious adverse reactions
TBI	total body irradiation
TCGA	The Cancer Genome Atlas
TE	treatment-emergent
TK	toxicokinetics
TPO	third-party organization
ULN	upper limit of normal

5. A Phase 1, Open-Label, Dose-Escalation Study of Olaratumab as a Single Agent and in Combination with Doxorubicin, Vincristine/Irinotecan, or High-Dose Ifosfamide in Pediatric Patients with Relapsed or Refractory Solid Introduction

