6.2.2. Study Completion and End of Trial

Any patient enrolled in Part A or Part B that has completed at least 1 cycle of treatment or discontinued due to an AE (during Cycle 1), and completed the required post-treatment safety assessment, will be considered to have completed the monotherapy portion of the study. Patients in Part A or Part B completing Cycle 1 who do not continue to Cycle 2 will be considered evaluable for monotherapy DLTs and PK. Any patient enrolled in Part A or Part B that has completed at least 2 cycles of treatment or discontinued due to an AE (during Cycle 2), and completed the required post-treatment safety assessment, will be considered to have completed the study. Any patient enrolled in Part C that has completed 1 cycle of treatment or discontinued due to an AE (during Cycle 1), and completed the required post-treatment safety assessment, will be considered to have completed the study. However, in all parts of the study, additional cycles of therapy may continue as long as the patient is receiving benefit and no criteria for discontinuation have been met. All secondary and exploratory endpoint analyses will be updated at study completion.

The end of trial occurs after the last patient has discontinued study treatment and completed any applicable follow-up.

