8.3. Efficacy Evaluations

A secondary objective of the study is to document any antitumor activity. Imaging studies and tumor assessments are to be obtained every 2 cycles (± 7 days), until documented progression for patients with complete response (CR), partial response (PR), or stable disease (SD).

For patients who have discontinued study treatment due to toxicity or reasons other than progressive disease, imaging studies and tumor assessments are to be obtained every 6 weeks (± 7 days) until progression. For these patients, details on subsequent anticancer treatment (start/stop dates and treatments administered) and first post-study treatment disease progression date should be recorded.

Each patient will be assessed by one or more of the following radiologic tests for tumor measurement:

- Computed tomography (CT) scan
- Magnetic resonance imaging (MRI)
- Chest x-ray

Each patient's full extent of disease will also be assessed with the following:

- Tumor measurement by RECIST v1.1 (Eisenhauer et al. 2009) should be used for all tumors with the exception of CNS tumors. RANO (Wen et al. 2010) or Macdonald (Macdonald et al. 1990) criteria should be used for CNS tumors.
- Evaluation of tumor markers, if indicated
- Evaluation of performance status (Lansky [Lansky et al. 1987] or Karnofsky [Karnofsky et al. 1948] scale)

To confirm objective responses, all lesions should be radiologically assessed, and the same radiologic method used for the initial response determination should be repeated at least 6 weeks (2 cycles) following the initial observation of an objective response, using the sample method that was used at baseline. If a patient is discontinued from the study, repeat radiology assessments may be omitted if clear clinical signs of progressive disease are present.

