Imaging Studies (CT/MRI)	X (if applicable)	X	For patients who have discontinued study treatment due to toxicity or reasons other than progressive disease, imaging studies and tumor assessments are to be obtained every 6 weeks (± 7 days) until progression or initiation of other anticancer therapy. RECIST v1.1 should be used for all tumors with the exception of CNS tumors; RANO or Macdonald criteria should be used for CNS tumors.
RECIST v1.1, RANO, or Macdonald Tumor Assessments	X (if applicable)	X	
Subsequent Anti-Cancer Treatments, and Associated Disease Progression Date		X	For all patients, details on subsequent anticancer treatment (start/stop dates and treatments administered) and first post-study treatment disease progression date should be recorded.
Other Assessments			
PK Sampling	X		See Attachment 4 for details.
Biomarker Sampling	X		

Abbreviations: AE = adverse event; CNS = central nervous system; CRF = case report form; CT = computed tomography; ECG = electrocardiogram; ECHO = echocardiogram; IRR = infusion-related reaction; MRI = magnetic resonance imaging; MUGA = multi-gated acquisition; PK = pharmacokinetics; RANO = Response Assessment in Neuro-Oncology; RECIST = Response Evaluation Criteria In Solid Tumors.

- a **Short-term follow-up** begins the day after the patient and the investigator agree that the patient will no longer continue study treatment and lasts approximately 30 days (± 7 days). The date of this agreement is to be reported on the CRF as the date of discontinuation from study treatment.
- b **Long-term follow-up** begins the day after short-term follow-up is completed. Patients that discontinue study treatment for reasons other than progression will be followed every 6 weeks (± 7 days) until progression.

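### Protocol 8.1.2.2.3 takes patients off study after Visit 801, against the 6-weekly imaging until progression required elsewhere, and the stated update of secondary endpoints does not cover long-term scans

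*Protocol*

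**What the plan says.** **Exit at Visit 801.** Protocol 8.1.2.2.3 places the safety assessments 30 ± 7 days "after the decision is made to discontinue the patient from the study". After them, "the patient will be discontinued from the study, unless there is an ongoing AE or SAE that is possibly related to study drug". For the excepted patients it adds: "In this instance, the patient should be followed in subsequent long-term follow-up visits until the event is resolved". The long-term visits described there serve adverse-event follow-up, and lack of progression is not an exception.

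**Imaging after stopping.** For patients who stop for toxicity or any reason other than progression, Protocol 8.3 says that "imaging studies and tumor assessments are to be obtained every 6 weeks", with a 7-day window, until progression. The synopsis says the same. The follow-up table in Attachment 1 agrees in footnote b: "Patients that discontinue study treatment for reasons other than progression will be followed every 6 weeks". The comment in that table stops imaging at a different point: "until progression or initiation of other anticancer therapy". Protocol 6.3.1 sends all patients who discontinue to the Study Schedule, which is Attachment 1.

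**Analysis timing.** Protocol 6.2.2 says: "All secondary and exploratory endpoint analyses will be updated at study completion". Section 4 defines that milestone: "This study will be considered complete after all patients have completed treatment and their safety summary visit". Section 6.2.2 also defines an end of trial that includes applicable follow-up, but ties no analysis to it.

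**PFS.** PFS is named in a secondary objective (Protocol 5.2.2). SAP 5.3.2 counts radiologic progression or death, with no restriction to the treatment period. SAP Table JGDN.5.1 censors a patient with neither at the last adequate radiological assessment, or at first dose.

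**The concern.** Take a patient who stops without progression and has no ongoing, possibly related event at Visit 801. Under 8.1.2.2.3 that patient leaves the study. Under 8.3 and Attachment 1 the same patient starts long-term imaging. Both cannot be followed, and two sites could each cite the protocol for opposite conduct.

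The patients lost would be those whose PFS is still open. Some such stops are planned: the Parts A and B schedules take doxorubicin and ifosfamide patients off study once the chemotherapy maximum is reached. Vincristine/irinotecan has no such maximum. Scans that were never taken cannot be recovered later.

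The analysis milestone has a smaller version of the same gap. It falls when the last patient has had the safety visit, so patients still in imaging follow-up at that date have later scans that no stated analysis picks up.

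**Working it through.** The documents give no power, event target or sample-size calculation for PFS, so there is no stated figure to reproduce. The check has three parts.

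**1. Does the Visit 801 window already capture a post-treatment scan?**
- Visit 801 assessments: 30 ± 7 days, so day 23 to 37 after the stop decision.
- Next 6-weekly scan, if the last scan was at the stop decision: 42 ± 7 days, so day 35 to 49.
- The overlap is days 35 to 37 only.

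Attachment 1 lists imaging at the short-term visit only where applicable. A patient discharged at Visit 801 would therefore usually have no post-treatment scan, and the censoring date would be the last on-treatment scan.

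**2. When do planned stops fall?**
- Doxorubicin: 6 cycles × 2 days × 37.5 = 450 mg/m². Ifosfamide: 6 × 5 × 2.8 = 84 g/m². Both match the stated limits.
- Parts A and B: 1 monotherapy cycle + 6 combination cycles = 7 × 3 = 21 weeks.
- Part C: six cycles would end at 6 × 3 = 18 weeks, but the Part C schedules do not state a stop of olaratumab at that point.

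**3. How much could be lost?**

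Inputs: n = 20, the target per combination arm in Protocol 6.2; T = 21 weeks; true medians m of 28.6 and 18.0 weeks, the two adult arms quoted in Protocol 5.3, plus 13 weeks as an assumed shorter value. Assumptions: exponential PFS, every patient observed to T, and no observation after T.

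Progression-free proportion at T: S(T) = 2^(−T/m). The Kaplan-Meier median is reached if at least 10 of the 20 patients have an event by T, so

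P(not reached) = P(X ≤ 9), X ~ Binomial(20, 1 − S(T)).

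| True median (weeks) | S(21) | P(median not reached) |
|---|---|---|
| 28.6 | 0.601 | 76% |
| 18.0 | 0.445 | 24% |
| 13 | 0.326 | 3% |

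If every patient did have a scan at the latest possible Visit 801, T = 21 + 37/7 = 26.3 weeks. The probability is then 52% for a median of 28.6 weeks and 7% for 18.0 weeks.

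**The case against.** The strongest reply is that 8.1.2.2.3 is a subsection on adverse-event reporting and was meant only to end safety collection. The synopsis, 6.3.1, 8.3 and Attachment 1 all point to continued imaging. The protocol also uses exit terms loosely: Visit 801 itself begins after the decision to discontinue the patient from the study, and in 6.2.2 patients in Parts A and B count as having completed the study after two cycles although they may continue therapy. As a reading of intent this is persuasive, and many sites would probably keep scanning. It does not remove the conflict. The sentence ends study participation, it allows one exception, and nothing gives Attachment 1 precedence.

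A reader might infer more than the text supports:
- *That the curves of the capped arms end about 30 days after the cap.* Censoring is at the last adequate scan, not at Visit 801. Nor does every patient necessarily stop at the cap: Protocol 6.2 allows olaratumab monotherapy after chemotherapy, 7.2.2 allows ifosfamide beyond 84 g/m² after consultation, and the instruction to stop at the maximum appears only in the Parts A and B schedules.
- *That the median would be inestimable.* The table gives probabilities. They are high only if PFS is near the better adult arm, which came from doxorubicin-naïve adults with soft tissue sarcoma. The documents give no PFS figure for relapsed or refractory paediatric tumours.
- *That late scans would never be analysed.* Section 6.2.2 states one update and does not bar another. The milestone is study-wide, so it affects only patients still in follow-up when the last safety visit occurs.
- *That a comparison between arms is biased.* None is planned. SAP 5.2 calls the analyses descriptive, and SAP 5.8 says the study was not designed to assess efficacy.

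**Conclusion.** The contradiction is real and lies in the current operative text. Followed literally, 8.1.2.2.3 would lose off-treatment progression and censor those patients at or near the end of treatment. The gap between study completion and end of trial is a second, smaller fault.

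The effect is confined to descriptive PFS and duration of response; the DLT and PK primary endpoint is untouched. The probabilities of about 76%, 24% and 3% describe the extreme case in which all 20 patients are unobserved after week 21. They rest on exponential PFS and on medians that are assumptions for this population. If most patients progress early, little is lost. The change should still be made, because it costs little and missing scans cannot be reconstructed.

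**What to change.** - **Protocol 8.1.2.2.3:** state that Visit 801 ends routine safety follow-up only. Patients without documented progression continue into the Attachment 1 long-term imaging follow-up unless they withdraw consent, die or are lost to follow-up. Keep the existing provision for ongoing related events.
- **Protocol 6.2.2:** tie the final update of PFS and duration of response to end of trial, or to a named cutoff that includes long-term imaging.
- **Attachment 1:** use one stop rule for off-treatment imaging in the comment and in footnote b. For PFS the choice matters little, since SAP Table JGDN.5.1 already censors at new anticancer treatment, but sites need a single instruction.
- **Continuing olaratumab after chemotherapy ends:** Protocol 6.2, 7.2.2 and the Parts A and B doxorubicin and ifosfamide schedules contradict each other. The sponsor must reconcile them, because the answer determines how many patients stop without progression and when.

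The imaging changes are wording only, since the scans are already scheduled. The price is that the final secondary analysis may come somewhat later.
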